The 3-month follow-up assessment will be identical for participants assigned to either the intervention or control group and will consist of: (1) completing the exit study report form, (2) a blood draw which will provide biological material for laboratory testing, and (3) a low-risk fitness assessment which does not involve any physical activity (Table 2). The exit study report form will

strongly resemble the original baseline study report form and query information pertaining to demographics, medical history, dietary composition, physical activity levels, mental health and wellbeing, as well as attitudes, feelings, and competency regarding genetic testing. Laboratory testing will not include genetic testing (as this would be completed using the blood samples collected at baseline) but will include testing of lipoproteins, fasting glucose, and inflammatory markers as conducted in the baseline assessment.

To incentivize study participants to complete their final assessment, they will receive: 1) an additional month's worth of exercise and meal plans and 2) a lifetime subscription to the GeneBlueprint web portal which will be updated with new genetic prediction scores and health tools over time. Furthermore, individuals in the control group will be provided access to their genetic results, personalized meal plan, and personalized workout plan upon trial completion.

Endpoints

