The primary endpoints will be changes in physical activity levels and healthy diet score from baseline to 3-month follow-up. Physical activity levels will be quantified based on survey responses to the following questions: (1) "In the last 3 months, how many times per week did you perform aerobic exercises?" and (2) "In the last 3 months, how many times per week did you perform strength training?" These two questions align with recommendations from the Canadian Physical Activity Guidelines, which split exercise into the two domains of aerobic exercise (150 minutes of moderate to vigorous activity per week) and strength training (2x per week). Dietary healthiness will be ascertained using the dietary risk score developed by the INTERHEART study which was found to explain 30% of the population attributable risk for acute myocardial infarction¹⁰. Briefly, the dietary risk score takes into account consumption of meat, salty snacks, fried foods, fruits and vegetables. Secondary endpoints will include cardio-metabolic markers (triglycerides, C-reactive protein, fasting glucose, blood pressure), measures of fitness (waist-to-hip ratio, circumference of thigh, calf, and bicep, body fat percentage) and cardio-metabolic risk as estimated by the validated INTERHEART modified risk score (IHMRS)¹¹.

Measurements and measurement instruments

a) Fitness and Physiologic Measurements

The same measurements will be taken at baseline and at 3-month follow-up (Table 2).

Table 2. Fitness and physiologic attributes and the corresponding measurement device.

Measurement(s)	Device
Systolic & Diastolic Blood Pressure	Sphygmomanometer
Resting Heart Rate	Stopwatch/Timer
Body Fat Percentage	Scale
Weight	Scale
Waist-to-Hip Ratio	Myotape measure
Circumference of thigh, calf, bicep, neck, and shoulder span	Myotape measure

b) Blood Collection & Laboratory Testing

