Blood testing results at baseline and 3-months follow-up could reveal medical diagnoses unbeknownst to the study participant that warrant disclosure. Such findings include but are not limited to diabetes (fasting glucose > 7 mmol/L), hypercholesterolemia (LDLc > 5 mmol/L), and hypertriglyceridemia (triglycerides > 10 mmol/L). Upon identification of an aberrant test result, confirmatory testing will be expedited through the Hamilton Regional Laboratory Medicine Program, which consists of several clinical laboratories approved by the Ontario Ministry of Health. Confirmatory testing will help mitigate the risk of false-positives, a potential source of unnecessary anxiety and stress for study participants. Once confirmatory testing validates the initial positive result, the study participant will be contacted by trial management and referred to the appropriate medical specialist (e.g. endocrinologist or lipid specialist). Continuation in the trial will be based on the physician's discretion as well as the willingness of the study participant.

Genetic Results

There is no risk of incidentally discovering medically actionable genetic conditions or disorders as this is beyond the scope of this project. While the American College of Medical Geneticists (ACMG) has recommended reporting pathogenic mutations within 65 genes that may cause conditions unrelated to the primary indications¹³, these recommendations specifically apply to studies involving clinical exome or genome sequencing. Our study does not involve clinical exome or genome sequencing and the proposed method is unable to detect variants of diagnostic value. Therefore, there is no risk of genetic incidental findings.

Fitness Assessment

Extremely elevated resting heart rate and blood pressure are contraindications for exercise. Incidental discovery of previously undiagnosed malignant hypertension (SBP > 180/120 mmhg) or tachycardia (resting heart rate > 100 bpm) during the baseline fitness assessment will preclude an individual from continuing with the fitness portion of the trial. Malignant hypertension is a medical emergency and anyone identified with this condition will be referred to the hospital immediately. Study participants identified with tachycardia will be referred to an appropriate health professional.

References

1. Roth, G. A. *et al.* Global, Regional, and National Burden of Cardiovascular Diseases for

- 10 Causes, 1990 to 2015. *J. Am. Coll. Cardiol.* **70**, 1–25 (2017).

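### The exercise stop for very high blood pressure or heart rate is written for baseline only, so a 3-month reading over the threshold leads to referral but does not hold the workout plan released next

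*Combined protocol and SAP*

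**What the plan says.** Under Incidental Findings, Fitness Assessment, the plan first gives a reason that is not tied to any visit: "Extremely elevated resting heart rate and blood pressure are contraindications for exercise". It then sets the thresholds (blood pressure above 180/120 mmHg, resting heart rate above 100 bpm) and the consequence: discovering either one "during the baseline fitness assessment will preclude an individual from continuing with the fitness portion of the trial". Two referral statements follow. For malignant hypertension, "anyone identified with this condition will be referred to the hospital immediately". For the other finding: "Study participants identified with tachycardia will be referred to an appropriate health professional".

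Under Measurements and measurement instruments, the text above Table 2 reads: "The same measurements will be taken at baseline and at 3-month follow-up". Table 2 lists both blood pressure and resting heart rate.

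Under Final assessment, participants who complete the exit visit are promised "an additional month's worth of exercise and meal plans". The same section adds that "individuals in the control group will be provided access to their genetic results, personalized meal plan, and personalized workout plan upon trial completion". Study Design confirms that controls have no workout plan before then.

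**The concern.** The stated reason for the stop applies to a reading at any visit, but the stop itself is written for one of the two visits at which the readings are taken. The uncovered visit comes immediately before the trial hands out exercise plans. For controls, the stop is therefore checked about 3 months before their first trial-supplied plan, and the newer reading has no written effect on whether they get it.

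What is at stake is participant safety. Someone whose exit reading meets the protocol's own contraindication could be referred and, at the same time, sent a programme of five 30-minute sessions a week. Participant Benefits and Risks lists exercise injury among the major risks of taking part.

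**Working it through.** The plan gives no figure on this point, so the check is a comparison of its sections.

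1. **When the readings are taken.** Table 2 and the sentence above it give two assessments, baseline and 3 months, with blood pressure and resting heart rate at each.
2. **When the stop applies.** The Fitness Assessment paragraph names baseline only. The stop covers 1 of the 2 assessments. No other visible section sets an exercise stop at 3 months.
3. **When referral applies.** Neither referral statement names a visit, so I read both as covering a 3-month finding.
4. **When plans are released.** Under Final assessment, workout plans go out after the exit visit: a first plan for controls, and an additional month for participants who complete the assessment. The Intervention section sets the plan at five 30-minute programmes a week.

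Putting these together for a control with a resting heart rate of 104 bpm (an illustrative value above the threshold of 100):

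| Visit of the reading | Referral | Effect on exercise under the written rule |
|---|---|---|
| Baseline | Yes | Barred from the fitness portion |
| 3 months | Yes | None stated; the workout plan falls due |

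The second row assumes that no unwritten step intervenes. The text does not say how controls' plans are released. The Randomization section says that the intervention is delivered by automated e-mail; if controls' plans go out the same way, there may be no natural point for staff to step in.

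**Ceiling on the number of people.** Power Calculations plans 250 per arm. At full retention, 250 + 250 = 500 participants could have a workout plan due after the exit reading, 250 of them controls receiving their first. With assumed retention of 90% or 80%, the totals are 500 × 0.9 = 450 or 500 × 0.8 = 400. These count everyone who completes the trial. The number affected is that total times the proportion over a threshold at 3 months, and the documents give no such proportion.

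**The case against.** The strongest defence is that the baseline-only wording is coherent. The stop bars a person from continuing with the fitness portion of the trial, and at the exit visit that portion is ending: monitoring finishes with the 3-month assessment and the gym membership runs for the trial's duration. What follows is a completion incentive and promised access. This explains the wording, but the trial still supplies the plans, and the stated contraindication does not lapse at exit.

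A reader might infer a drafting slip from the laboratory paragraph, which does name both visits: "Blood testing results at baseline and 3-months follow-up could reveal medical diagnoses". The documents do not support that firmly. The laboratory rule concerns confirmation, disclosure and referral; it holds no plan and leaves continuation to the physician and the participant. Its fitness counterpart is the referral statements, and on referral the two rules match at 3 months.

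Other parts of the defence also stand:

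- Referral, including immediate hospital referral for malignant hypertension, is the main safety response and already applies.
- Staff could use the general contraindication statement to advise against exercise.
- Controls have had gym access and an orientation since baseline, and intervention participants have already had 3 months of plans. Holding a plan does not by itself prevent exercise.
- Participants are screened healthy adults who have passed the baseline stop.
- Participants are told to ask a trainer about, or skip, any exercise that feels uncomfortable. This helps, but it depends on how the participant feels and does not act on a measured reading.

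What remains is narrow: at baseline the protocol requires a stop as well as referral, and at exit only the referral is written.

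**Conclusion.** The gap is real and minor. Following the text, a participant over the threshold at 3 months is referred but still receives the workout plan then due, although the protocol says that such readings contraindicate exercise.

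Three stronger readings are not supported:

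- **That such a person gets no response.** Referral applies at either visit.
- **That 500 participants are at risk.** That figure is the largest number of people who could have a plan due after the exit reading. The number over a threshold is unknown and, in this population, probably small.
- **That the trial's results are compromised.** The plans at issue follow the 3-month measurements, so no endpoint, analysis or conclusion changes.

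The conclusion assumes that the referral statements cover both visits and that no rule elsewhere holds the plan. Figure 1, the consent form and the information sheet are not visible and could contain one. I rate this a cheap improvement of low priority.

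**What to change.** Leave the baseline sentence as it is. Merely adding the 3-month visit to it would achieve little, because there is almost no fitness portion left to stop at exit. Instead, add one sentence to the Fitness Assessment paragraph under Incidental Findings:

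> If either finding is made at the 3-month assessment, the participant is referred as above and advised not to exercise, and any workout plan due after that assessment is withheld until the participant confirms to the study team that the treating clinician has cleared exercise; meal plans, genetic results and portal access are released as planned.

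Confirmation by the participant is used because the plan describes no report back from the fitness referral. The rule is the same in both arms and acts after the exit measurements, so sample size, outcome assessment and the intention-to-treat analysis stay as they are.

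The cost is a delayed workout plan for each affected participant and a small administrative step to record clearance and release the plan. One asymmetry remains: the same reading bars a participant at baseline, with no written route back, but only delays the plan at exit. That is acceptable, because at exit only the plan release is left to control.
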